8. Privacy: Participation in research may involve a loss of privacy. To prevent this, research records will be kept as confidential as possible. Only a code number will identify the individual research records. The code number will not be based on any information that could be used to identify the subject (for example, social security number, initials, birth date, etc.) The master list linking names to code numbers will be kept separately from the research data. All research information will be kept in locked files at all times. Subject identity will not be revealed in any reports or publications resulting from this study. Only authorized research staff will have access to the information gathered in this study.

While filling out study forms, or during the psychiatric examination, some participants may feel uncomfortable disclosing personal thoughts and feelings. Careful efforts aimed at maintaining confidentiality have been effective in previous research, and only participants' code numbers will be recorded on the forms themselves to protect confidentiality.

9. Selection: Interested subjects will have the study briefly described over the telephone, and if interested, they will be asked to answer a brief tobacco use history and medical screening questionnaire. If subjects are eligible for the study based on the telephone screening, they will be invited to come to the clinic for a screening evaluation. The screening evaluation will include the following: a) obtaining informed consent; b) smoking history and assessment of nicotine dependence using the Fagerstrom Test of Nicotine Dependence (FTND) c) complete physical and psychiatric examination including the structured clinical interview (SCID) for DSM-IV; d) laboratory examination including complete blood count, liver and kidney function tests, and glucose; e) urine analysis, drug screen, and for women, urine pregnancy test and f) urinary cotinine and urine menthol glucuronide levels.

10. Recruitment: A total of 210 smokers will be recruited from the New Haven area by newspaper advertisements and fliers.

11. Research Plan

A. Overview

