We are proposing a double-blind, placebo-controlled study that enrolls young adult smokers stratified for menthol preference. Menthol and control flavor will be delivered via an e-cigarette just prior to saline or IV nicotine infusion. This menthol / nicotine reinforcement study was preceded by a separate menthol dose-finding study that determined the low and high doses of menthol to be administered by the e-

[Type text]

[Type text]

cigarette. For this dose-finding study, subjects were screened at the West Haven site where the IV nicotine study will be performed, but the dose-finding study was conducted at the John Pierce Labs located on the Yale Campus located about 2 miles from the West Haven site. The screening procedure for the dose-finding study was described in a separate screening consent form. The dose-finding study did not administer any nicotine.

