14:00 noon	HR/BP, EKG, M-NWSC, BQSU, SAFTEE

[Type text]

[Type text]

15:00 PM	End of session, collection of urine sample, blood draw Discharge
----------	---

*The same measures will be obtained following saline and each nicotine administration. For brevity, only the measures after saline are shown. Abbreviations: CO: Alveolar carbon monoxide; HR/BP: Heart rate/Blood pressure; EKG: Electrocardiogram; M-NWSC: Minnesota Nicotine Withdrawal Symptom Checklist; BQSU: Brief Questionnaire of Smoking Urges; DEQ: Drug Effects Questionnaire; SAFTEE: Systematic Assessment for Treatment Emergent Events.

12. Data analysis methods

Data analyses: The primary analyses will be intent-to-treat and will include all available data on subjects who complete at least one test day. Mixed-effects models will be used to test the study hypotheses. These models allow for different numbers of observations per subject, use all available data on each subject, and are unaffected by randomly missing data. They also provide flexibility in modeling the correlation structure of the data. All data will be checked for normality and transformations will be applied as necessary. Significance level of 0.05 will be used for the main hypotheses and Bonferroni correction will be applied for post-hoc tests.

Specific Aim #1: To determine if menthol administered via e-cigarettes will change the reinforcing effects of pure nicotine administered intravenously in cigarette smokers who smoke mentholated or non-mentholated cigarettes. The reinforcing drug effects will be measured with the DEQ.

Hypothesis #1A: Concurrent menthol and nicotine administration will lead to greater reinforcement than nicotine and control flavor, saline and menthol, or saline and control flavor conditions.

Hypothesis #1B: Enhancement of nicotine reinforcement by menthol will be greater in menthol smokers than in non-menthol cigarette smokers.

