The main outcome measures will be the “good effects” and “drug liking” items of the DEQ. Mixed effects models will include the within-subject factors nicotine dose (0.25, 0.5 mg nicotine or placebo), menthol dose (low dose of menthol, high dose of menthol, or control flavor) and time of measurement (+1,+3,+5,+10,+15,+30,+45,+55 minutes); the between-subject factor types of cigarette preference (menthol vs. non-menthol) and all possible interactions among these factors. We will also consider order effects for nicotine dose (1, 2 or 3) and session day (1, 2 or 3) and the effects of potential covariates (race, sex, baseline plasma NMR, FTND scores). These effects will be included in the final model if significant. Estradiol and progesterone levels will also be considered as potential covariates in a secondary analysis of women only. We will consider several different correlation structures for the repeated measures within individuals, and will select the best fitting one based on Schwartz Bayesian information criterion. SAS PROC MIXED will be used for the mixed-model analyses.

A significant interaction between nicotine dose and menthol dose, with significantly higher response to menthol + nicotine compared to control flavor + nicotine or control flavor + saline will be considered supportive of hypothesis 1A. A significant interaction between nicotine dose, menthol dose, and group (menthol vs. non-menthol smokers), with significantly stronger effects in menthol smokers than in non-menthol smokers, will be considered supportive of hypothesis 1B. We expect significant effects for both doses and will also test for dose-dependent effects.

[Type text]

[Type text]

Rationale for sample size: Both studies have 80% power to detect large effect sizes ($f=0.4$) for the interactions of interest in repeated measures analysis with 30 subjects per group for a total of 60 subjects at 0.05 significance level. Our preliminary data for both outcome measures show larger magnitude effects for the nicotine effects (all $f>0.5$) and menthol effects are expected to be similarly strong (Sofuoglu et al. 2009a). Applying Bonferroni correction and using an alpha level of 0.01 we have 80% power to detect post-hoc comparisons of medium to large effect size $d'=0.7$ for the menthol and nicotine effects. Our previous study shows larger effects of nicotine $d'>1.0$. To account for up to 70% dropout we will recruit 160 subjects for a target of 60 completers.

13. Risks and benefits

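### 160 recruits at 70% dropout leave 48 completers, not the 60 that Section 12 claims, and Section 10's total of 210 is not reconciled with 160

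*Protocol*

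**What the plan says.** Section 12 (Data analysis methods, Rationale for sample size) claims 80% power for large effects (f = 0.4) on the interactions of interest, "with 30 subjects per group for a total of 60 subjects at 0.05 significance level". The paragraph ends with the recruitment figure: "To account for up to 70% dropout we will recruit 160 subjects for a target of 60 completers".

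Section 10 (Recruitment) gives another number: "A total of 210 smokers will be recruited from the New Haven area by newspaper advertisements and fliers".

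Two other places bear on how these are read. Section 12 (Data analyses) says that the primary analyses "will include all available data on subjects who complete at least one test day", so the analysis is not confined to completers. Section 11.A (Overview) says that this study "was preceded by a separate menthol dose-finding study". The protocol gives no sample size for that earlier study.

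**The concern.** Section 12 puts the dropout allowance, the recruitment number and the completer target in one sentence, and they do not fit together. The power claim is stated for 60 subjects, and the recruitment figure is there to secure that number in the worst case the authors allow for. It falls short of doing so.

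The second total, in Section 10, adds to the problem. An ethics board, the DSMB (which receives recruitment reports) or site staff cannot tell from the protocol whether recruitment ends at 160 or at 210. That number determines how many people are exposed to intravenous nicotine and when enrolment closes.

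**Working it through.** **Inputs.** From Section 12, Rationale for sample size: 60 completers (30 per group), dropout d up to 0.70, 160 recruits. From Section 10: 210 recruits.

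**Attempt to reproduce 160.**
- Correct inflation, N / (1 − d): 60 / 0.30 = 200.
- Common mistaken inflation, N × (1 + d): 60 × 1.70 = 102.

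Neither gives 160. The figure comes out only with d = 0.625, since 60 / 0.375 = 160.

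**What each total delivers.**

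| Recruits | Completers at 70% dropout | Largest dropout that still leaves 60 |
|---|---|---|
| 160 (Section 12) | 160 × 0.30 = 48 | 1 − 60/160 = 62.5% |
| 200 (needed) | 200 × 0.30 = 60 | 70% |
| 210 (Section 10) | 210 × 0.30 = 63 | 1 − 60/210 = 71.4% |

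At 70% dropout, 160 recruits fall 60 − 48 = 12 completers short (12/60 = 20%). That leaves 24 per group if losses are equal. In recruits, the shortfall is 200 − 160 = 40. The two stated totals differ by 210 − 160 = 50.

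**Illustration of power at 60 and 48.** The protocol does not give the repeated-measures correlation, the degrees of freedom or the timing of dropout, so its 80% cannot be reproduced. The figures below use assumed tests and show only how far the answer depends on that choice. The F-tests use a noncentral F distribution with λ = f²N, or λ = f²N × 3/(1 − ρ) for the repeated-measures version with 2 groups and 3 measurements. The paired tests use a noncentral t with noncentrality d√n.

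| Assumed test | 60 completers | 48 completers |
|---|---|---|
| Between-subject F, f = 0.4, α = 0.05, 1 df | 86% | 77% |
| Between-subject F, f = 0.4, α = 0.05, 2 df | 78% | 67% |
| Within-between repeated measures, f = 0.4, α = 0.05, ρ = 0 to 0.5 | above 99% | above 99% |
| Paired t in one group, d = 0.7, α = 0.01 (n = 30; 24) | 85% | 73% |
| Paired t in the pooled sample, d = 0.7, α = 0.01 (n = 60; 48) | 99.6% | 98.2% |

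Under some of these assumptions, 48 completers fall below 80%; under others the loss is negligible.

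**The case against.** The strongest case on the other side accepts the arithmetic and disputes its weight.

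- **70% is an upper bound.** With 160 recruits, 60 completers are still reached at any dropout up to 62.5%. This is true, but the sentence claims cover up to 70%, and between 62.5% and 70% it does not provide it.
- **Power may hardly change.** The interactions the protocol powers are within-subject (nicotine by menthol) or within-between (nicotine by menthol by group). The between-subject F-tests match neither, and the within-between formula stays above 99%. This stands: no definite loss of power can be claimed, and the finding does not rest on one.
- **The mixed model uses partial data.** Anyone with at least one completed test day is analysed. Each session includes all three infusions, so even a one-day subject informs the nicotine contrast. The analysed number would be as low as 48 only if every dropout left before finishing a first test day. This also stands. However, each menthol condition is given on a different day, so a one-day subject contributes no within-subject menthol contrast. Partial data cannot be assumed to replace the 12 missing completers, and Section 12 sets its own target in completers.
- **210 may be a wider count**, for example one that includes dose-finding subjects, who were screened at the same VA site under the same criteria. That is possible, so the 160/210 difference is an unreconciled ambiguity and not a proven contradiction. Against this reading, Section 10 speaks of recruitment still to come, while the dose-finding study is described as finished and has no stated size. In any case, the meaning of 210 cannot change 160 × 0.30.

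**Conclusion.** The concern holds. The 48 completers, the 200 recruits needed and the 62.5% tolerated dropout follow from the protocol's own numbers, with no outside assumption. The figure of 24 per group also assumes equal losses in menthol and non-menthol smokers. The gap of 50 between the two recruitment totals is unexplained. That 210 covers 70% dropout and 160 does not suggests that 160 may be a leftover figure, but the protocol does not say so.

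The effect on power is undetermined. The 48 is a completer count and not necessarily the analysed number. The correction is still required, because the sample-size rationale relies on a recruitment figure that is wrong as written.

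**What to change.** State one recruitment number in Sections 10 and 12, and say what it counts: consented or randomised, with or without dose-finding subjects. If the two numbers count different things, define each. Then choose one of two routes:

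1. If 210 refers to this study, carry it into Section 12. It covers 70% dropout with 63 completers; the minimum for 60 is 200.
2. If 160 is kept, restate the tolerated dropout as 62.5%. Add that 48 completers are expected if dropout reaches 70%, and give the power under the planned mixed model for that case.

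The change is to protocol wording only. The first route adds no enrolment beyond the total already in Section 10. The second adds none either, but commits the study to a lower tolerated dropout.

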Potential risks:

There are potential risks, discomforts and inconveniences associated with participation in this study. These may be due to nicotine or menthol administration, blood drawing, other study procedures and potential loss of confidentiality.

1) Common side effects of nicotine include nausea, vomiting, heartburn, and elevated heart rate and blood pressure. Toxic doses of nicotine may cause abdominal pain, hyper salivation, diarrhea, dizziness, confusion, hearing and vision problems, syncope, seizures, hypotension, irregular pulse, and death. However, these toxic effects occur at doses 40 to 50 times that which will be used in our study. Other potential risks from this study include administering a drug that has addictive potential.

2) Menthol administration produces typical sensory effects in the mouth and throat. The doses of menthol that are found in cough drops, ranging 1 to 10 mg are regarded to be safe (Sweetman, 2011). In spite of ubiquitous use of menthol in a wide range of products, only few cases of menthol poisoning has been described in the literature following very high doses of menthol ingestion, 200 mg or more. Menthol poisoning reported to cause ataxia, confusion, coma, nausea, and vomiting. However, these toxic effects occur at doses 20 to 30 times that which will be used in our study.

3) The combination of intravenous nicotine and inhaled menthol has not been previously examined to the best of our knowledge. We have no reason to believe there is an increased risk from the combination used in this study as compared to the widespread use of mentholated cigarettes, menthol e-cigarettes or smoking while using a menthol-containing lozenge. However, the administrations will be closely monitored for any signs that this unique combination of IV nicotine and inhaled menthol results in unexpected findings.

4) Propylene glycol and vegetable glycerin are categorized by the FDA as compounds that are Generally Recognized As Safe (GRAS). They are both commonly used ingredients in food products, pharmaceuticals and in personal care products. They are also now used as the base liquid ingredient for e-cigarettes. Although e-cigarettes are reported to be helpful for smoking cessation, the FDA has not approved e-cigarettes for this use, and the long-term consequences of e-cigarette use have not been assessed.

[Type text]

[Type text]

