In order to participate in a study, each subject must give informed consent. All potential risks will be described in detail to the subjects in the consent form. The personnel in the laboratory have been certified in either Advance Cardiac Life Support (ACLS) or Basic Life Support. If a problem arises, the subject will be treated immediately.

Confidentiality in this study is of the utmost importance to us. All information obtained will be stored in coded form. The names of the subjects will be used in hospital records.

The risk associated with participating in this study is moderate, because the nicotine administered may be associated with mild side effects. Serious side effects associated with this treatment are not expected. This project will be monitored by the Center's Data and Safety Monitoring Board (DSMB) because the study involves double-blind treatment of smokers with nicotine. This board is composed of persons not otherwise affiliated with the clinical study who are experienced in various aspects of the conduct of clinical trials for the treatment of addictive disorders. The Yale TCORS Independent Data Safety Monitoring Board includes experts in the field of tobacco use behaviors and challenge studies (Chair: [name], FRCPC, Professor and Co-Director, Division of Brain and Therapeutics, Dept. of Psychiatry, U of Toronto; [name], Professor and Chair, Department of Health Outcomes & Behavior, H. Lee Moffitt Cancer Center & Research Institute) and in statistics ([name], Assistant Professor of Neurobiology, Columbia University). The members of the DSMB, and all study Investigators, will complete Conflict of Interest forms created by Yale's IRB in accordance with NIH guidelines.

We will report recruitment, follow-up, and adverse events to this panel on a bi-annual basis with serious adverse events reported within 48 hours. Prior to study initiation, critical parameters for collection of side effects and for study discontinuation will be recommended to the DSMB who may use these or other measures to monitor safety of the ongoing trial. The DSMB will be available to convene outside of scheduled meetings, if necessary, due to concerns regarding a particular subject or due to any troublesome developments in subjects' experiences during the study. The DSMB will make appropriate recommendations for changes in the study protocol, if needed.

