This monitoring will be consistent with NIH policy regarding the protection of human subjects in research, and FDA guidance on statistical practices for clinical trials (ICH E9) and good clinical practices (ICH E6). In general, the data to be reviewed will include screening data, baseline data, efficacy data, and

[Type text]

[Type text]

safety data.

The Principal Investigator will conduct a review of all adverse events and determine the attribution and grade of severity of the adverse event by using the following scales:

Attribution of Risk Categories:

Definite: Adverse event(s) will clearly be related to investigational agent(s) or other intervention

Probable: Adverse event(s) will likely be related to investigational agent(s)

Possible: Adverse event(s) may be related to investigational agent(s)

Unlikely: Adverse event(s) will doubtfully be related to investigational agent(s)

Unrelated: Adverse event(s) will clearly not be related to the investigational agents(s)

Grades of Risk:

0: No adverse event or within normal limits

1: Mild adverse event

2: Moderate adverse event

3: Severe adverse event resulting in hospitalization or prolongation of existing hospitalization, a persistent or significant disability/incapacity, or a congenital anomaly/birth defect

4: Life-threatening or disabling adverse event

5: Fatal adverse event

Serious adverse events (SAEs) include any untoward medical occurrence that at any dose results in death or the immediate risk of death, hospitalization or the prolonging of an existing hospitalization, persistent or significant disability/incapacity or a congenital anomaly/birth defect. Subjects will be terminated from participation if the investigator feels that subjects' health or well-being may be threatened by continuation in the study. Serious unanticipated and anticipated adverse events will be reported within 48 hours to the VA Hospital, Yale IRB, the DSMB, and NIH. We will directly report to the FDA, whenever their magnitude or frequency exceeds expectations.

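### Grade 3 is defined by seriousness outcomes and the SAE list has no medically-important-event item, so a non-life-threatening toxic event treated on the unit has no grade above 2 and no required report before the bi-annual one

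*Protocol*

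**What the plan says.** All of this is in the Protocol, mostly in section 13 (Risks and benefits).

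- **Severity scale (Grades of Risk).** The Principal Investigator assigns each event a grade of severity. Grade 1 is mild. The grade 2 entry is only "2: Moderate adverse event", with no criteria. Grade 3 is "3: Severe adverse event resulting in hospitalization or prolongation of existing hospitalization, a persistent or significant disability/incapacity, or a congenital anomaly/birth defect". Grade 4 is "4: Life-threatening or disabling adverse event". Grade 5 is fatal.
- **SAE definition (directly below the scale).** It opens with "Serious adverse events (SAEs) include any untoward medical occurrence that at any dose results in death or the immediate risk of death" and continues with "hospitalization or the prolonging of an existing hospitalization, persistent or significant disability/incapacity or a congenital anomaly/birth defect". Nothing else is listed.
- **Reporting (Protection of Subjects).** Adverse events go to the DSMB "on a bi-annual basis with serious adverse events reported within 48 hours". Serious events also go to the VA hospital, the IRB and NIH within 48 hours. The board may meet off schedule if necessary, and safety parameters are to be recommended to it before the study starts.
- **Named toxicity (Potential risks, item 1).** The effects listed for toxic doses of nicotine include "dizziness, confusion, hearing and vision problems, syncope, seizures, hypotension, irregular pulse, and death". The protocol adds that these arise at 40 to 50 times the study doses.
- **Ending participation (section 11.C and Study Procedures, item c).** A subject is withdrawn on fixed blood pressure or heart rate limits, or on signs and symptoms of nicotine toxicity. Neither place links withdrawal to any report.

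**The concern.** Severity and seriousness answer different questions. Severity describes how intense an event was. Seriousness describes its outcome and decides how fast it is reported. Here the grade for severe events repeats outcomes from the SAE list, so an intense event without one of those outcomes has no grade of its own. The SAE list has no item that would catch such an event by another route.

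The setting makes this foreseeable. Sessions take place on a hospital unit with a physician present and life-support-certified staff who treat problems at once, so toxicity resolved on site without admission is a plausible course. The protocol also says that intravenous nicotine with inhaled menthol has not, to the team's knowledge, been studied before, and it promises to watch for unexpected findings. A toxicity event that ends a subject's participation is exactly such a signal, yet the written rules can record it as moderate at most and do not require the board to hear of it promptly.

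**Working it through.** The protocol gives no figure of its own on this point, so the main check is textual: apply the written scale and the SAE list to each kind of event.

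1. **Syncope or irregular pulse, treated on the unit, not life-threatening, no admission, no disability.** Grade 3 requires hospitalization, disability or birth defect, and none applies. Grade 4 requires a life-threatening or disabling event, and neither applies. The highest grade left is 2. No SAE item is met, so the 48-hour route does not open. The required report is the bi-annual one, whether or not participation ended under section 11.C.
2. **The same event, but life-threatening.** It is grade 4 wherever it is treated. If there is immediate risk of death it is also an SAE, due within 48 hours. No gap.
3. **The same event, followed by admission.** It fits grade 3 if severe, and it is an SAE. No gap.
4. **Persistent or significant disability.** It fits grade 3 by that wording and grade 4 as disabling, and no rule chooses between them. It is an SAE under either grade, so reporting is unaffected.
5. **Death.** Grade 5 and an SAE. No gap.

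The gap is therefore case 1. Case 4 is a grading ambiguity only.

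**Exposure during the longest delay.** Inputs:
- Nicotine infusions per completer: 2 per Test Session × 3 sessions = 6 (section 11.A).
- Duration: about 2.5 years = 5 half-years (section 20).
- Subjects: 60 target completers and 160 recruits (section 12, Rationale for sample size); 210 recruits (section 10).

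Formula: infusions per half-year = subjects ÷ 5 × 6.

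- 60 completers only: 60 ÷ 5 × 6 = 72
- 160 recruits, full attendance: 160 ÷ 5 × 6 = 192
- 210 recruits, full attendance: 210 ÷ 5 × 6 = 252

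The 72 leaves out infusions given to subjects who attend only part of the study, so it is a floor. The 192 and 252 assume that every recruit attends everything, although section 12 plans for up to 70% dropout, so they are upper extremes. All three assume even accrual, an event just after a bi-annual report and no off-schedule meeting.

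**The case against.** A reader might infer that every named toxic event treated on the unit stays at grade 2 or below and reaches the board only twice a year. The protocol does not support that. A seizure or hypotension can be life-threatening, which is grade 4, and "death or the immediate risk of death, hospitalization or the prolonging of an existing hospitalization" are SAE criteria wherever treatment takes place. The board can also convene off schedule over a single subject or a troublesome development.

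Other points on that side:

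- **The SAE list is introduced by a word that can be read as non-exhaustive.** True, but it gives the investigator no further criterion to apply.
- **Off-schedule meetings and pre-study safety parameters exist.** True. The meetings are discretionary, no trigger or deadline is stated, and the content of the parameters is not given. A board cannot convene over an event it has not been told about.
- **The overlap of grades 3 and 4 has no reporting consequence.** This stands.
- **No misgrading has been shown.** A brief faint that resolves may well be moderate, and grading is left to the Principal Investigator. This stands for such an event, but an investigator who judged it severe would still have no grade above 2 to assign.
- **Such events should be rare.** The protocol places toxicity at 40 to 50 times the study doses and reports more than 400 smokers given intravenous nicotine with no adverse event attributed to it. This limits the expected number of cases. It also keeps the burden of prompt reporting small and makes any single case more informative.
- **No text in the protocol requires a medically-important-event item.** True. The case for adding one rests on the protocol's own toxicity list and its own rule for ending participation, which at present lead to no prompt report.

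**Conclusion.** The point holds in a limited form. As written, the scale leaves a severe event with no grade above 2 unless it is life-threatening, disabling or has a grade 3 outcome, and it gives disability two possible grades. For toxic events of the kind the protocol names that are treated on the unit and are not life-threatening, hospitalized or disabling, no report to the DSMB is required before the bi-annual one, even when participation has been ended.

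The size is a delay of up to about six months instead of 48 hours, during which roughly 72 to 252 nicotine infusions could be given under the assumptions shown. This is exposure in a worst case, not an expected harm. The point concerns safety classification and oversight. It does not touch the primary analysis or the sample size. It should be corrected, because the written rules, followed exactly, produce the gap and the remedy is cheap.

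**What to change.** Amend the wording of section 13:

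- Define grades 1 to 4 by intensity, with grade 3 as a severe event whether or not hospitalization follows, and keep grade 5 as fatal.
- Remove hospitalization, disability (including the disabling wording in grade 4) and birth defect from the grade scale, and keep them only in the SAE definition. This also removes the overlap of grades 3 and 4.
- Add a medically-important-event item to the SAE definition.
- State that the DSMB is notified on the 48-hour route whenever participation is ended for signs of nicotine toxicity.

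The cost is a wording amendment and a few more expedited reports. No dose, stopping limit or analysis changes.
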